**Criteria for Evaluation:**

Safety:

Safety criteria are identical to those in the main Study ZX008-1503 and include AEs, laboratory safety parameters (hematology, chemistry, urinalysis), vital signs (blood pressure, heart rate, temperature, and respiratory rate), physical examination, neurological examination, 12-lead ECGs, Doppler ECHOs, and body weight.

Efficacy:

The primary criteria for evaluation in the sub-study is the change over time in the 5-point Likert Ease of Use Questionnaire to measure user experience.

Secondary exploratory efficacy criteria for evaluation include change over time in the following:

- Perceived Stress Scale (PSS) to measure caregiver burden.
- Correlation of monthly (28-day) convulsive seizure count between the Embrace watch and seizure diary.
- Size of EDA response during and in the post-ictal hour of convulsive seizures.
- Skin-surface temperature (measured on wrist).
- Frequency of fever-related convulsive seizures.
- Comparison of convulsive seizure count during periods of sleep, and during the combined titration and maintenance periods, between the Embrace watch and seizure diary.
- Correlation of convulsive seizure time and classification as determined by Embrace watch and seizure diary.
- EQ-5D-5L to measure quality of life of the parent/caregiver while using the Embrace.
- HADS to measure affective symptoms of the parent/caregiver while using the Embrace.

All other efficacy criteria are identical to those in the main Study ZX008-1503.

**Sample Size Determination:** This sub-study is designed as a pilot exploratory study to provide preliminary information on the ease of use of the Embrace watch to detect seizures in outpatients with Dravet syndrome, therefore, the sample size is based more on feasibility than on power to detect differences.

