**Statistical Methods:**

All safety data will be summarized as described in the ZX008-1503 protocol and associated Statistical Analysis Plan. Efficacy analyses for sub-study participants that rely on the ERT seizure diary or that are specific to the Embrace watch will not be included in the main ZX008-1503 analyses. Exploratory data for the Embrace watch system data will be processed as follows:

- Embrace's automated convulsive seizure detection results will be manually compared to the diary counts of convulsive seizures. Cohen's Kappa values will be computed for agreement.

- The above will be repeated separately for events during periods of sleep vs. events while awake, based on Embrace’s determination of sleep/wake (periods of sleep will be based on actigraphy and EDA as measured by the Embrace watch).
- For each seizure detected by the Embrace watch, the peri-ictal EDA recording will be segmented from 60 minutes before detected seizure onset to 120 minutes afterward. A “significant EDA response” is declared when an increase in skin conductance level of more than 2 times the standard deviation of the pre-ictal baseline occurs. Significant EDA responses will be analyzed in terms of the amplitude of their EDA\_peak, the response duration, defined as the difference between “EDA\_end” and “EDA\_start,” and the natural logarithm of the area under the curve (AUC) of the rising phase (from “EDA\_start” to “EDA\_peak”) and of the total response (from “EDA\_start” to “EDA\_end”), ie, LogAUCrise and LogAUCtot. These measures will be examined to see if they vary over time with the treatment.
- Skin-surface temperature changes will be averaged daily and compared over time, with separate comparisons made for “seizure-free” periods and for “pre-seizure periods.” The duration of these periods will be based on average 60-minute intervals, but may also be examined with shorter intervals.
- Each episode of fever, defined as any body temperature above 98.6°F (37°C), and number, severity, and duration of each seizure detected by Embrace will be correlated to dose of study drug.

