### 1.2 RATIONALE FOR CURRENT SUB-STUDY, ZX008-1503-SS01

This is a sub-study to the ZX008-1503 OLE trial, which will include up to 20 participants who are enrolled in Study ZX008-1503. This is an exploratory sub-study to provide preliminary information on the overall usability and performance of the Empatica Embrace watch system (Embrace) in outpatients with Dravet syndrome.

Seizure frequency is the primary outcome measure for individual treatment and for clinical trials. The current gold standard for demonstrating efficacy of new anti-epileptic drugs is a 50% reduction in seizure frequency. This efficacy standard is based on patients or their caregivers maintaining seizure diaries.

Use of sensitive seizure detection technology may allow greater accuracy in seizure counting. Seizure detection technology may also provide means to address specific clinical questions, such as the occurrence of unwitnessed seizures during periods of sleep.

The Embrace has been designed for automated convulsive seizure detection and characterization. The Embrace watch monitors electrodermal activity (EDA) and accelerometer-sensed changes in motion to analyze the information and detect patterns that are typically observed in convulsive seizures in real-time. The data can then be used to compare seizure detections, false alarms, and seizures that are not detected, to e-diary seizure report information.

This sub-study for patients enrolled in the open-label extension study may provide insights into seizure triggers, such as temperature, or facilitate seizure counts during sleep and allow for comparison of various endpoints captured by the Embrace to the same endpoints captured in an electronic hand-held seizure diary.

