### **2.2 SECONDARY OBJECTIVES**

The secondary exploratory objectives of the study are:

- To compare objective convulsive seizure count, as captured by the Embrace, to convulsive seizure count captured manually in the electronic seizure diary.
- To compare objective convulsive seizure count during periods of sleep, as captured by the Embrace, to convulsive seizure count during periods of sleep captured manually in the electronic seizure diary.
- To examine if the size of the electrodermal activity (EDA) response during and after a convulsive seizure is reduced over time with ZX008 treatment.
- To examine if skin-surface temperature changes with ZX008 treatment.
- To examine if skin-surface temperature levels are different during periods of time preceding convulsive seizures than during times that are seizure-free.
- To examine correlation of study drug dose and fever-induced convulsive seizure frequency, severity, and duration.
- To examine the timing of diary-reported events vs. automatically detected events.
- To assess quality of life while using the Embrace system with the following measures:
  - Quality of Life (QoL) of the parent/caregiver using the EQ-5D-5L scale.
  - Affective symptoms of the parent/caregiver using the Hospital Anxiety and Depression Scale (HADS).
- To assess caregiver stress using the Perceived Stress Scale (PSS).

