#### **8.3.2 Efficacy Analysis**

The primary criteria for evaluation in the sub-study is the change over time in the 5-point Likert Ease of Use Questionnaire to measure user experience.

Secondary exploratory efficacy criteria for evaluation include change over time in the following:

- Perceived Stress Scale (PSS) to measure caregiver burden.
- Correlation of monthly (28-day) convulsive seizure count between the Embrace watch and seizure diary.
- Size of EDA response during and in the post-ictal hour of convulsive seizures.
- Skin-surface temperature (measured on wrist).
- Frequency of fever-related convulsive seizures.
- Comparison of convulsive seizure count during periods of sleep, and during the combined titration and maintenance periods between the Embrace watch and seizure diary.
- Correlation of convulsive seizure time and classification as determined by Embrace watch and seizure diary.
- EQ-5D-5L to measure quality of life of the parent/caregiver quality of life while using the Embrace.
- HADS to measure affective symptoms of the parent/caregiver while using the Embrace.

All other efficacy criteria are identical to those in the main Study ZX008-1503.

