#### **8.4 STATISTICAL METHODS**

All safety data will be summarized as described in the main Study ZX008-1503 protocol and associated Statistical Analysis Plan. Efficacy analyses for sub-study participants that rely on the ERT seizure diary or are specific to the Embrace will not be included in the main Study ZX008-1503 analyses. Exploratory data for the Embrace watch system data will be processed as follows:

Continuous data will be summarized using descriptive statistics including means, standard deviations, medians, lower and upper quartiles, and ranges. Categorical variables will be summarized with frequencies and percentages. Confidence intervals will be calculated for key parameters or estimates as warranted.

A complete description of the statistical analyses and methods will be available in the Statistical Analysis Plan, which will be finalized before the database is locked.

The primary analysis will rely on descriptive statistics to summarize responses to the Ease of Use Questionnaire from each time point where the questionnaire is administered. In particular, the modal, ie, most frequent, response to each item on the questionnaire will be reported at each time point. Responses across all items on the questionnaire will be summed to create an overall index that will also be reported at each time point.

Exploratory data for the Embrace watch system data will be processed as follows:

- Embrace’s automated convulsive seizure detection results will be manually compared to the diary counts of convulsive seizures. Spearman rank correlation will be used to quantify agreement.
- The Spearman rank correlation described above will be repeated separately for events during periods of sleep and for events while awake, based on Embrace’s determination of sleep/wake (periods of sleep will be based on actigraphy and EDA as measured by the Embrace watch).

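### Spearman correlation is named as the measure of watch-diary agreement but cannot show whether the counts match in level; the synopsis names an undefined kappa instead, and off-watch seizures have no rule

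*Combined protocol and SAP*

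**What the plan says.** The first secondary objective in Section 2.2 is "To compare objective convulsive seizure count, as captured by the Embrace, to convulsive seizure count captured manually in the electronic seizure diary"; a second asks the same for sleep, and another is "To examine the timing of diary-reported events vs. automatically detected events". Section 1.2 says the data can be used to "compare seizure detections, false alarms, and seizures that are not detected, to e-diary seizure report information".

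The evaluation criteria (synopsis and Section 8.3.2) include both a correlation, "Correlation of monthly (28-day) convulsive seizure count between the Embrace watch and seizure diary", and a comparison, "Comparison of convulsive seizure count during periods of sleep, and during the combined titration and maintenance periods between the Embrace watch and seizure diary". They also list a correlation of seizure time and classification between the two sources.

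For method, Section 8.4 has the detections compared manually with diary counts and adds that "Spearman rank correlation will be used to quantify agreement". This "will be repeated separately for events during periods of sleep and for events while awake", with sleep and wake decided by the watch. In the synopsis, under Statistical Methods, the same manual comparison, also split by sleep/wake, ends differently: Cohen's "Kappa values will be computed for agreement".

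On wear, inclusion criterion 6 (Section 4.1) expects daily charging and allows seizures that occur off the watch to be entered manually in the record, without saying which record. Section 8.2.2 admits a subject to the Embrace population on one week of valid watch data. Section 8.4 leaves the complete methods to a SAP due before database lock; that SAP is not among the documents supplied.

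**The concern.** The objective asks whether two counts are the same. The named statistic asks whether subjects fall in the same order on both. A report that followed Section 8.4 literally could present a high rho as agreement when the watch counted about half, or nearly twice, what the diary did.

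The synopsis does not resolve this. Kappa needs a unit to be rated and a set of categories, and neither is given. With two named methods for one comparison, the choice could end up being made after the data are seen.

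The missing rule for non-wear adds a second ambiguity: a low watch count could be read as poor detection when it reflects hours off the wrist.

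**Working it through.** **Inputs.** From the documents: up to 20 subjects; 28-day counts; Spearman (Section 8.4); kappa (synopsis). The documents state no power, precision, seizure rate, detection rate or false-detection rate, so there is no figure to reproduce. Every rate below is an assumption.

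**Step 1: level blindness, no simulation needed.** Rho is the correlation of rank(D) with rank(E), where D is the diary count and E the watch count. If E = c × D with c > 0, the ranks are identical and rho = 1. On 20 illustrative counts from 1 to 60, with Lin's concordance coefficient for contrast:

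| c | rho | E/D | concordance |
|---|---|---|---|
| 0.5 | 1.00 | 0.5 | 0.64 |
| 2 | 1.00 | 2.0 | 0.64 |
| 3 | 1.00 | 3.0 | 0.40 |

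**Step 2: random capture, no false detections.** Subject rate = median × exp(SD × Normal); true count = Poisson(rate); diary = Binomial(true, a); watch = Binomial(true, b), independently; n = 20. Case A has a = b = 0.7, so the ratio is 0.7/0.7 = 1.0. Case B has a = 0.5 and b = 0.9, so the ratio is 0.9/0.5 = 1.8. Mean rho:

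| Median per 28 days | log-SD | A (ratio 1.0) | B (ratio 1.8) | Gap |
|---|---|---|---|---|
| 3 | 0.5 | 0.776 | 0.745 | 0.031 |
| 10 | 0.5 | 0.862 | 0.839 | 0.023 |
| 20 | 0.5 | 0.908 | 0.890 | 0.018 |
| 40 | 0.5 | 0.941 | 0.929 | 0.012 |
| 3 | 1.0 | 0.881 | 0.857 | 0.024 |
| 10 | 1.0 | 0.941 | 0.929 | 0.012 |
| 20 | 1.0 | 0.963 | 0.955 | 0.008 |
| 40 | 1.0 | 0.977 | 0.972 | 0.005 |

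Rho varies far more with the spread of seizure rates than with the ratio. Against that, an observed rho of 0.8 with n = 20 has a 95% interval of about 0.50 to 0.93 (Fisher z, SE = sqrt((1 + rho²/2)/17)). A gap of 0.03 could not be seen.

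**Step 3: add false detections.** Take a complete diary, 50% detection, and a mean of 0.2 false detections per day (0.2 × 28 = 5.6 per period), varying exponentially between subjects. Over the same eight scenarios mean rho is about 0.26 to 0.91. The 95% half-width of the 12-week pooled ratio is about 0.07 to 0.91, against 0.02 to 0.07 without false detections. At median 10 and log-SD 0.5 the expected ratio is roughly 0.5 + 5.6/(10 × exp(0.125)) = 0.5 + 5.6/11.33 = 0.99 (simulated 1.00), while rho is about 0.49. A ratio near 1 here hides a watch that misses half the seizures and makes up the number with false ones. Level and rank can therefore each mislead alone.

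**Step 4: kappa.** Kappa = (p_o − p_e)/(1 − p_e), where p_o is observed and p_e chance agreement over a fixed set of rated units. For seizure events the protocol defines no unit in which neither source reports a seizure, so the both-negative cell has no value and kappa cannot be computed as written.

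**Step 5: non-wear.** Suppose seizures are spread evenly over the day and off-watch seizures enter only the diary. Then ratio = detection × hours worn/24. A ratio of 0.5 fits 60% detection at 20 h (0.6 × 20/24) and 100% detection at 12 h (1.0 × 12/24). If off-watch seizures are entered in the Embrace record instead, this relation fails and the two sources are no longer independent. The protocol does not say which applies.

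**The case against.** Several points on the other side have weight.

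- **Deferral.** Section 8.4 hands the full methods to a later SAP, which could settle all of this. That stands, and it limits the point to the protocol text. It does not remove the conflict between two methods already named.
- **Spearman has a place.** One might infer that it is simply the wrong statistic. The documents do not support that: one criterion is explicitly a correlation of 28-day counts, and Spearman fits it. The mismatch is with the agreement label, the count-comparison objective and the sleep-count comparison.
- **Other text helps.** One might also infer that the plan ignores level and individual events. Not quite. The manual comparison and the general means and medians of Section 8.4 would show a level gap if applied to both counts, and the time-and-classification criterion presupposes some pairing of events. But no difference, ratio or matching method is specified.
- **There is a data-validity rule.** The one-week requirement in Section 8.2.2 bears on wear, but it governs who is analysed. It does not say which diary seizures count, and valid is not defined.
- **Consequence is small.** This is a feasibility-sized pilot; the comparison is secondary and exploratory and stays out of the main-study analyses. That stands.

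**Conclusion.** The concern holds as a point about the protocol text. Spearman alone cannot meet the count-comparison objective, two current sections name different methods for one comparison, and non-wear has no counting rule. The level blindness is exact: rho = 1.00 at any constant ratio. The gap of at most about 0.03 between ratios of 1.0 and 1.8 is illustrative and assumes no false detections.

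Two stronger readings should be resisted. First, rho will not always look high: with the assumed false detections it falls as low as about 0.26, so a misleadingly high rho is possible, not certain. Second, a pooled ratio is not an adequate replacement by itself. It nets missed seizures against extra ones, and no claim is made that it is precise with 20 subjects. Nor can the effect of non-wear be sized until the protocol says where off-watch seizures are recorded.

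This should be corrected before the SAP is final. The primary ease-of-use analysis is unaffected.

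**What to change.** 1. Name the same method in Section 8.4 and the synopsis. Delete kappa, or define its rated unit and categories.
2. Keep Spearman as a descriptive correlation of 28-day counts and stop calling it agreement. Add the per-subject 28-day difference (watch minus diary) with limits of agreement, overall and by sleep/awake. Support it with the pooled watch/diary ratio and a subject-clustered interval.
3. Where diary onset times are available, report the percentage of diary seizures matched within a pre-stated window and the unmatched Embrace detections per 24 h worn. This separates misses from extras and also serves the time-and-classification criterion. Call the latter unmatched, not false, because the diary may itself miss seizures.
4. State which record receives off-watch seizures, report them separately, and restrict the comparison to worn time if wear can be recovered from the stored signals.

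**Cost.** Item 1 is wording. Item 2 uses counts already collected and needs a little programming. Item 3 depends on diary times: the timing objective and the sleep split imply them, but Section 3.1 lists only number and type of seizures. Item 4 depends on whether the signals show wear, which the protocol does not state; if they do not, report the overall comparison with that limitation.

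**Downsides.** Matching is sensitive to diary time error. The pooled ratio is dominated by high-rate subjects: the top 4 of 20 supply about 36-54% of events in the assumed scenarios. Clustered intervals can undercover with 20 subjects (89-95% in simulations without false detections).

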### 6.2.2.1 Embrace Alert App

The Embrace Alert app detects events from user physiology, such as a convulsive seizure, and sends an alert to a caregiver through a phone call or text message. Real-time seizure detection and alerting is still experimental and is for investigational use only. It also collects raw data from Embrace hardware and sends it to a receiver (smart phone memory) and consequently to a cloud storage system for later retrieval. The Alert app runs on an iPod Touch and must remain in close proximity of the patient. The Alert app is also used for device configuration (eg, setting the clock and activating/deactivating night-mode which suppresses interactions) and firmware management.

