- For each seizure, the peri-ictal EDA recording will be segmented from 60 minutes before detected seizure onset to 120 minutes afterward. A “significant EDA response” is declared when an increase in skin conductance level of more than 2 times the standard deviation of the pre-ictal baseline occurs. The time of the beginning of such an EDA response is defined as “EDA\_start,” the time of the maximum peak of the EDA response is defined as “EDA\_peak,” and the point in time following this peak, when the EDA falls below 10% of the peak amplitude is defined as “EDA\_end.” Significant EDA responses will be analyzed in terms of the amplitude of their EDA\_peak, the response duration, defined as the difference between “EDA\_end” and “EDA\_start,” and the natural logarithm of the area under the curve (AUC) of the rising phase (from “EDA\_start” to “EDA\_peak”) and of the total response (from “EDA\_start” to “EDA\_end”), ie, LogAUCrise and LogAUCtot. These measures will be examined to see if they vary over time with the treatment. Each of the measures will be evaluated for changes over time using a mixed model repeated measures (MMRE) that allows for a different intercepts for each subject (ie, a random effect) but a common slope over time (ie, a fixed effect).
- Skin-surface temperature changes will be averaged daily and compared over time, with separate comparisons made for “seizure-free” periods and for “pre-seizure periods.” The duration of these periods will be based on average 60-minute intervals, but may also be examined more with shorter intervals. Changes in skin-surface temperature over time will be evaluated using similar MMREs as described above for EDA endpoints.

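### The EDA trend analysis uses every Embrace detection without diary confirmation, so a changing share of false alarms can bias the slope in either direction

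*Combined protocol and SAP*

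**What the plan says.** The objective in Section 2.2 is "To examine if the size of the electrodermal activity (EDA) response during and after a convulsive seizure is reduced over time with ZX008 treatment". It concerns convulsive seizures, not device alarms.

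The analysis unit is a detection. The synopsis (Statistical Methods) reads "For each seizure detected by the Embrace watch, the peri-ictal EDA recording will be segmented from 60 minutes before detected seizure onset". Section 8.4 drops the reference to the watch but keeps the same anchor: "For each seizure, the peri-ictal EDA recording will be segmented from 60 minutes before detected seizure onset to 120 minutes afterward". A seizure known only from the diary has no detected onset, so the Section 8.4 rule also works on detections.

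A detection contributes to the size measures (peak, duration, LogAUCrise, LogAUCtot) only if there is an "increase in skin conductance level of more than 2 times the standard deviation of the pre-ictal baseline occurs". Each measure then goes into a mixed model with a random intercept per subject and one slope over time shared by all subjects. The model has no term for whether a detection was confirmed.

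The plan accepts that detections can be wrong. Section 1.2 says the data can be used to "compare seizure detections, false alarms, and seizures that are not detected, to e-diary seizure report information", and Section 6.2.2.1 says "Real-time seizure detection and alerting is still experimental and is for investigational use only". In Section 8.4 the diary is used for count agreement. Nothing there links it to the EDA analysis.

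**The concern.** The slope is meant to describe how the EDA response to a convulsive seizure changes on ZX008. The events that feed it are a mixture of true seizures and false alarms. If the proportions of that mixture change over time, the mean of the mixture changes too, even when the response per true seizure is constant. A random intercept removes differences between subjects in average level. It does not remove a change in the true/false mix within a subject.

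Such a change is plausible. The sub-study covers the first 12 weeks of the extension, with the option to extend to 24 weeks, and Section 3.1 describes titration from a starting dose. If true seizures became less frequent while false alarms did not, the false-alarm share would rise. A slope in either direction could then be read as a change in autonomic response when it reflects only which events were counted.

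**Working it through.** The plan states no false-alarm rate, EDA effect, alpha or power, so there is no figure of its own to reproduce. The check asks how far the slope could move under stated assumptions.

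**Inputs from the documents:** up to 20 subjects; 12 weeks; the 2 SD entry rule; random intercept with common slope. Section 1.2 cites a 50% reduction in seizure frequency as a general efficacy benchmark. It is used here only as a scenario.

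**Assumed:** T = 10 true detections per 28 days at the start; f = false alarms per 28 days, constant over time; q = chance that a false alarm passes the 2 SD rule (true seizures taken as 1); d = mean response in true seizures minus mean response in false alarms, in within-subject SD units.

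**Step 1, mixture arithmetic.** False-alarm share s = f·q / (f·q + T). Apparent shift = -(s_end - s_start)·d.

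For f = 10, q = 1 and a 50% fall in true seizures: s_start = 10/(10+10) = 0.50 and s_end = 10/(10+5) = 0.667. The shift is -0.167 SD at d = 1, 0 at d = 0 and +0.083 SD at d = -0.5.

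Other cases with a 50% fall and d = 1:

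| f | q | share, start to end | shift (SD) |
|---|---|---|---|
| 2 | 1 | 17% to 29% | -0.12 |
| 30 | 1 | 75% to 86% | -0.11 |
| 10 | 0.1 | 9% to 17% | -0.08 |

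Over falls of 25% to 75%, f from 2 to 30 and q from 0.1 to 1, the shift at d = 1 runs from -0.01 to -0.33 SD. It is 0 if seizures do not fall.

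**Step 2, simulation of the planned model.** 20 subjects, 12 weekly blocks, seizures falling linearly, subject seizure rates varying around 10 per 28 days, subject-intercept SD 0.7, within-subject SD 1, no real EDA change, 200 runs per scenario. Slopes are the change over 12 weeks. The 5% two-sided test is a yardstick of this check, not a test the plan declares.

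| Fall | f | q | d | slope (SD) | rejections |
|---|---|---|---|---|---|
| 50% | 10 | 1 | 1 | -0.16 | 33% |
| 50% | 10 | 0.5 | 1 | -0.14 | 17% |
| 50% | 10 | 0.1 | 1 | -0.07 | 9% |
| 50% | 2 | 1 | 1 | -0.10 | 7.5% |
| 50% | 30 | 1 | 1 | -0.10 | 24.5% |
| 50% | 10 | 1 | 0.5 | -0.08 | 11.5% |
| 50% | 10 | 1 | 0 | 0.00 | 3% |
| 50% | 10 | 1 | -0.5 | +0.08 | 11.5% |
| 0% | 10 | 1 | 1 | -0.01 | 3.5% |

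With 200 runs the margin around 5% is 1.96·√(0.05·0.95/200) = 3.0 points, so rates from about 2% to 8% cannot be told from nominal.

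**Step 3, after the change.** For the first row, restricting to confirmed detections with perfect matching gives a slope of +0.01 SD and 2% rejections.

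**The case against.** A reader might infer that the plan will produce a spurious fall in EDA response. The documents do not support that. A fall needs three things at once: fewer true seizures during the sub-study, a roughly constant false-alarm rate, and smaller EDA responses in the false alarms that pass the 2 SD rule. None is documented. The 50% figure is a general benchmark, not a forecast for these weeks, and entrants have already completed a core study. Wear time may vary, and the false-alarm rate with it. The detector uses EDA together with motion (Section 1.2), so false alarms may carry EDA rises as large as true seizures or larger. This objection stands: the direction is open.

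A reader might also infer that the 2 SD rule does no filtering. That goes too far. It may remove some false alarms, and the bias shrinks if it removes most of them (q = 0.1 above). Nor does the text say that the same detections define the pre-seizure periods for skin temperature. Their source is not stated.

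Further points on the other side: Section 8.4 could be read as meaning true seizures that the watch also detected; the sub-study is an exploratory pilot sized on feasibility; and complete methods are left to a Statistical Analysis Plan to be finalized before database lock. The first fails because no rule says how a true seizure is recognized. The others limit the weight of the point and show where the rule can be written. They do not supply it.

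**Conclusion.** The point holds in conditional form. As written, unconfirmed detections enter an estimate about convulsive seizures, and a change in the false-alarm share can bias the common slope for EDA peak, duration and LogAUC. The direction depends on how large the responses in false alarms are. In the illustrative case the shift is about -0.16, 0 or +0.08 SD, and across the downward scenarios examined it runs from -0.01 to -0.33 SD at d = 1. All of these rest on assumed seizure rates, false-alarm rates and response sizes, so the true size is unknown.

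The absence of a confirmation rule is plain from the text. Confidence that it matters in practice is moderate. The consequence is confined to interpreting one secondary exploratory objective, and the change is cheap enough to be worth making.

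**What to change.** In Section 8.4 and the synopsis:

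- Run the EDA model on Embrace detections matched to a convulsive seizure in the ERT diary within a pre-specified time window. The comparison of diary and detection times already planned in Sections 2.2 and 8.3.2 can supply the matching.
- Report the all-detections model alongside it.
- Tabulate the share of unmatched detections by 28-day period (three periods in 12 weeks, six if extended to 24).
- State that a fall in EDA will be interpreted as a treatment-related change only if both analyses agree. Agreement is necessary, not sufficient, because all subjects receive ZX008.
- For skin temperature, state what defines the pre-seizure periods. If detections are used, apply the same matched and all-detections pair.

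The cost is wording, one further model run per measure and one table. Matching has a downside: it drops real but unwitnessed seizures, notably in sleep, which Section 1.2 gives as a reason for using the device. The diary is also not fully independent, because the app alerts the caregiver who completes it. That is why both analyses should be shown.

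### The EDA criterion covers the seizure and the post-ictal hour, but the method sets no latest time for the start or peak of the response, so a weak response can be measured from outside that window

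*Combined protocol and SAP*

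**What the plan says.** The evaluation criterion, worded alike in the synopsis and Section 8.3.2, is "Size of EDA response during and in the post-ictal hour of convulsive seizures". The objective in Section 2.2 is looser: it asks whether the response "during and after a convulsive seizure is reduced over time with ZX008 treatment", with no one-hour limit.

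Section 8.4 takes a recording that "will be segmented from 60 minutes before detected seizure onset to 120 minutes afterward"; the synopsis gives the same segment. A significant response is declared when "an increase in skin conductance level of more than 2 times the standard deviation of the pre-ictal baseline occurs". In Section 8.4, EDA_start is the beginning of such a response; "the time of the maximum peak of the EDA response is defined as" EDA_peak; and the later point "when the EDA falls below 10% of the peak amplitude is defined as" EDA_end. None of the three has a latest permitted time, and nothing links the 120-minute segment to the one-hour criterion.

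For significant responses only, four measures are analysed: peak amplitude, duration, LogAUCrise and LogAUCtot. Each goes into a mixed model with a random intercept per subject and a common slope over time.

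**The concern.** The criterion and the method describe different windows. As Section 8.4 is written, a rise that begins or peaks 100 minutes after onset meets the definition, although it lies outside the criterion for any seizure shorter than 40 minutes (100 − 60).

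The plan treats EDA as varying with state, since Section 8.4 uses it with actigraphy to separate sleep from wake. A late rise therefore need not belong to the seizure.

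The objective is to see whether responses shrink over time. If they do, a late rise is more likely to supply the peak. LogAUCrise (start to peak), duration and LogAUCtot (both start to end) would then partly describe the later rise.

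**Working it through.** The documents give no expected size, SD, power or error rate for the EDA measures, so there is no plan figure to reproduce. The check has four steps.

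**1. Window arithmetic.** For a seizure of d minutes the criterion ends d + 60 minutes after onset, and the segment ends at 120. The share of the post-onset segment outside the criterion is (60 − d)/120:
- d = 1: 59/120 = 49%
- d = 10: 50/120 = 42%
- d = 30: 30/120 = 25%
- d = 60: 0%

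Seizure durations are assumptions.

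**2. Chance crossings.** With independent epochs, P(at least one value above mean + 2 SD) = 1 − (1 − 0.0228)^k. For 5-minute epochs, k = 12 within 62 minutes gives 24%, and k = 24 within 120 minutes gives 42%. For 1-minute epochs the figures are 76% and 94%.

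**3. Simulation, maximum of the whole segment.** Assumed: 20,000 one-minute autoregressive series per setting, a 60-minute baseline, a 2-minute seizure, and a true response peaking at 5 minutes and decaying with a 15-minute time constant. A response is declared if the post-onset maximum minus the baseline mean exceeds 2 baseline SDs. Correlation time and true response are varied.

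| Correlation time (min) | True response (SD) | Declared, 62 min | Declared, 120 min | Peak after post-ictal hour | Mean peak, 62 / 120 min |
|---|---|---|---|---|---|
| 2 | 0 | 67% | 83% | 48% | 2.489 / 2.625 |
| 2 | 2 | 96% | 97% | 12% | 3.163 / 3.193 |
| 2 | 4 | 100% | 100% | 0.3% | 4.629 / 4.630 |
| 10 | 0 | 53% | 69% | 49% | 2.282 / 2.428 |
| 10 | 2 | 84% | 88% | 17% | 2.833 / 2.871 |
| 10 | 4 | 99% | 99% | 1.4% | 4.214 / 4.216 |
| 30 | 0 | 50% | 64% | 52% | 1.914 / 2.094 |
| 30 | 2 | 85% | 88% | 16.5% | 2.481 / 2.536 |
| 30 | 4 | 99% | 99% | 1.1% | 4.056 / 4.059 |

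At 1 SD the late share is 29–36%; at 8 SD it is 0%. With a 3-minute seizure and correlation times of 5–60 minutes, the late share at 2 SD is about 14–17%.

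Amplitude at 2 SD: 3.193/3.163, 2.871/2.833 and 2.536/2.481 are increases of 0.9%, 1.3% and 2.2%. For a fall in true response from 4 to 2 SD (correlation time 10 minutes), mean peak drops by 4.214 − 2.833 = 1.381 with the one-hour limit and by 4.216 − 2.871 = 1.345 without it. The long window hides 1 − 1.345/1.381 = 2.6% of the drop.

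LogAUCrise for the same fall (correlation time 10 minutes) changes by only about 0.04 with the 120-minute window, against about 0.22 with the limit. Most of the change is lost.

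**4. Simulation, first crossing.** Here the response runs from the first 2-SD crossing until EDA falls below 10% of its peak, so a later separate rise is not part of it. The late share is about 3–6% at 2 SD (at most 7% in any setting tried), under 0.5% at 4 SD, and 22–39% with no true response. LogAUCrise is little affected.

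**The case against.** The text is silent about late rises; it does not say that they count. It states how much recording to cut around the seizure and then defines the start, peak and end of a response. Recording beyond one hour has an obvious use: following the decay to EDA_end. The objective says only during and after the seizure. Taking the maximum of the whole segment is the worst-case reading. Section 8.4 defers full methods to an SAP to be finalized before database lock, and this is one of several exploratory criteria in a feasibility-sized sub-study of up to 20 subjects.

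All of this stands, and it limits the size of the point. It does not remove it. The criterion names the post-ictal hour in two places, no sentence reserves the extra time for EDA_end, and the text does not say which rise is used when there are several.

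A reader might infer something stronger: that the plan does measure unrelated EDA activity as the seizure's response, and so would hide a reduction in response size under ZX008. The documents do not support that. They do not state that late rises are accepted or that a late rise is unrelated to the seizure; late peaks are unrelated in the simulation only by construction. Peak amplitude, the most direct measure of size, barely moves.

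**Conclusion.** The mismatch is real and can be read directly from the text: the criterion ends one hour after the seizure, and the method sets no latest start or peak within 120 minutes of onset. A rise or peak outside the criterion's window can be measured as the seizure's response.

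The effect is confined to weak responses, about 2 baseline SDs or less, and depends on the reading. It is about 14–17% of declared peaks at 2 SD under the whole-segment maximum (12% at the shortest correlation time tried) and about 3–6% under first crossing. At 4 SD it is about 2% or less. Amplitude bias at 2 SD is about 1–3%.

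LogAUCrise can be materially masked under the whole-segment reading. Duration and LogAUCtot are exposed because they run to an end point defined from the peak, but their bias was not computed. The percentages rest on assumed seizure length, autocorrelation and response shape, so they indicate order of size only. The point is minor, and worth making because the correction is nearly free.

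**What to change.** In Section 8.4 and the synopsis, require EDA_start and EDA_peak to fall between detected onset and 60 minutes after seizure end, and use the remaining time to 120 minutes only to locate EDA_end. State how seizure end is obtained; the synopsis already refers to the duration of seizures detected by the device.

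Because the models include only significant responses, also report over time the proportion of seizures with no significant response in that window. Otherwise the smallest responses drop out unseen.

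If the sponsor does intend 120 minutes, change the criterion in the synopsis and Section 8.3.2 to match.

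The cost is a sentence or two and one extra summary, with no new data. Fewer responses will be declared. The limit does not remove chance 2-SD crossings within the hour: with no true response, the simulated share declared falls only from 64–83% to 50–67%.
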